4.0 Study Endpoints (if applicable)

The primary endpoints are changes in responses on various clinical measures pre- and post-intervention: the Social Responsiveness Scale, the Social Skills Improvement System, the Quality of Play Questionnaire, the Aberrant Behavior Checklist, and the Test of Adolescent Social Skills Knowledge-Revised. We predict that participants receiving active tDCS will show greater improvement in these measures compared to those receiving sham tDCS. This will be assessed using non-parametric t-tests (IBM SPSS Statistics, Chicago, IL) conducted separately for each measure.

Secondary endpoints will be fMRI response and reaction time pre- and post-intervention on a laboratory test of attention and social information processing.

The primary safety endpoint will be self-reported adverse effects of tDCS collected after each treatment session.

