10.0 Study Design / Methods

We will conduct brain stimulation with 17 randomized adolescent participants at initial enrollment. Drop-outs are expected, with the goal of having 10 youths with ASD complete the study, with the same number of parents actively participating by the end of the experiment.

The following table summarizes the schedule of activities for a subject:

Schedule of events	Activities	Time commitment for volunteer	Compensation
Initial visit with research coordinator, Drs. [name] and [name]	Consent (parent and child)	15 min	\$25 (child) \$15 (parent)
	Medical & MRI screening (parent and child)	5 min	
	ADOS-2 & KBIT-2 (with child), clinical measures (with parent)	90 min	

	Mock scanner training with child	10-15 min	
	fMRI scanning with child	30 min	
	tDCS acclimation with child	10 min	
PEERS weekly sessions	PEERS training plus active / sham tDCS	1 hr / week x 14 weeks	\$15 per session (child) \$0 (parent)
Post-intervention visit	clinical measures (with parent), fMRI scanning (with child)	45 minutes	\$25 (child) \$25 (parent)
14-week follow-up visit	clinical measures completed online (by parent)	30 minutes	\$10 (child) \$50 (parent)

Parents will make initial phone or email contact with the study coordinator. The study coordinator will conduct a brief telephone screening to determine preliminary eligibility for the study. If eligible, the study coordinator will schedule the initial visit.

The initial visit will last approximately 3 hours. Following informed consent (see Section 9.0), an in-depth MRI screening form will be filled out by the parent and the medical history information obtained during the initial telephone interview will be reconfirmed. Any female participants will complete a pregnancy test. [name] will then conduct the ADOS and K-BIT with the child while the parent completes the following clinical outcome measures on a computer (using RedCap) in a separate room: Social Responsiveness Scale-2 [26], the Social Skills Improvement System, the Quality of Play Questionnaire, the Aberrant Behavior Checklist, and the Test of Adolescent Social Skills Knowledge-Revised [27]. The child and parent are given a 10-minute break and a healthy snack, if desired.

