Pre- and post-treatment fMRI sessions will use a task in which two visual stimuli are presented simultaneously then removed, with the location of one image replaced by a probe[28]. Participants respond with the index or middle finger of the preferred hand to indicate the probe location. In this type of probe task, brain activation is expected to be higher for probes that are in the same location as the stimulus that is attended more. Reaction time is also expected to be faster if the probe appears in a location that was just recently attended compared to the location that was not attended. In one condition, the stimuli are a face and house to assess attentional bias to faces versus non-faces (related to social awareness). Another condition presents a face with direct gaze and one with averted gaze (related to social motivation, social anxiety). These conditions are implemented in functional runs lasting 5 minutes each and each run is repeated twice. The runs are presented in counterbalanced order across subjects. Following fMRI scanning, an additional tDCS acclimation session is completed. Electrodes are placed on the scalp again, and current is gradually increased to the desired level over a 5-minute period. The child will watch a movie or play a video game during this acclimation period.

Following the baseline visit, subjects will return on a different day for the PEERS training. PEERS is a parent-assisted intervention that teaches targeted social skills to high-functioning patients with ASD during fourteen weekly sessions. Parents and adolescents attend separate concurrent sessions that instruct them on key elements about making and keeping friends.

Each adolescent PEERS session begins with a didactic section, approximately 30 minutes in duration. Then the group conducts role plays modeling the correct and incorrect ways to utilize the weekly skill set. Next, the group reviews homework from last week and then discusses homework for next week. During the last 10-15 minutes of the session, the adolescents and parents are reunified to discuss the homework assigned for next week.

Each parent session begins with a detailed review of each adolescent's progress on the previous week's homework. Then the parents are given didactic information about the weekly skills set. Finally, the parents are reunified with the adolescents in order to discuss the plan for completion of assigned homework for next week.

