Subjects will receive tDCS weekly in conjunction with their PEERS session. Half of the adolescent participants will be randomly assigned to receive active tDCS of the left dorsolateral prefrontal cortex (DLPFC), and half will receive sham tDCS to the same location. Active / sham assignment does not change over the course of the experiment. However, within each condition, half of the participants will receive tDCS during the first 30 minutes and half will receive tDCS during the second 30 minutes. This schedule will then be reversed at each session. This will counterbalance the time of tDCS delivery and will increase the feasibility of setting up tDCS in a reasonable time window. Sham tDCS is achieved by wiring all group participants to separate computer-controlled tDCS programs. All participants receive an initial brief dose; those receiving sham treatment are then automatically decreased to zero by the computer, allowing all clinical personnel to remain blind to the participant's condition. Participants themselves are also blind to condition as most people report that the tingling sensation associated with tDCS decreases within the first few minutes of treatment.

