A brief questionnaire about adverse effects will be completed with participants and their parents immediately following the second and last treatment sessions. Tolerance for tDCS will be monitored during tDCS delivery by noting the frequency with which a subject reported irritation, discomfort, burning or pain, whether a subject attempted to remove the tDCS leads, whether a subject wished to discontinue the procedures due to the tDCS (rather than the PEERS training). After the second and last PEERS sessions, the experimenters will administer a brief questionnaire with the subject about whether they felt uncomfortable itching, tingling, burning during the session or whether they have had headaches, neck pain, sleepiness, moodiness in the past week. Any of these effects will be recorded. We will conclude that tDCS can be tolerated if these effects are experienced less than 25% of the time for a given individual. We will also report on how many subjects tolerated the procedures.

The child and parent receive compensation in the form of gift cards following each visit to MUSC (see Table above).

After 14-weeks of PEERS training, subjects will return for a post-treatment session in which the clinical outcome measures will be completed by parents and fMRI session will be completed by the participants (same procedures as before excluding tDCS acclimation).

Finally, 14 weeks after the post-treatment session, the parent will be sent a reminder via RedCap to complete the clinical outcome measures. In addition, both parent and child will be asked to guess which condition the child was assigned to (active or sham tDCS). Once the final follow-up surveys are completed in RedCap, the final gift card of \$75 is mailed to the family.

Information about which condition a subject was assigned to is not typically provided, but if a subject asks, we can tell them after all study procedures are completed and the blind is lifted. Study personnel will also be asked to guess the condition before the study blind is lifted.

Source records: the data collected from subjects include: parental and subject responses on clinical tests and questionnaires, anatomical and functional MRI scans, reaction time and accuracy responses on the fMRI task.

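### The parent, the only described rater of the five primary measures, may be taken through the child's stimulation-sensation questionnaire before the post-treatment rating, and is not named as masked

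*Combined protocol and SAP*

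**What the plan says.** **Who rates.** Section 4.0 states: "The primary endpoints are changes in responses on various clinical measures pre- and post-intervention". It lists five: the Aberrant Behavior Checklist, the Quality of Play Questionnaire, the Social Skills Improvement System, the Social Responsiveness Scale and the Test of Adolescent Social Skills Knowledge-Revised. Section 10.0 has the adolescent tested at baseline "while the parent completes the following clinical outcome measures on a computer (using RedCap) in a separate room", and all five are then named. At the post-treatment visit "the clinical outcome measures will be completed by parents".

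**Who answers the adverse-effect questionnaire.** Section 10.0 says: "A brief questionnaire about adverse effects will be completed with participants and their parents immediately following the second and last treatment sessions". A few lines later, with the same timing, it says "the experimenters will administer a brief questionnaire with the subject about whether they felt uncomfortable itching, tingling, burning during the session", and adds past-week symptoms such as headache and sleepiness. This second sentence does not mention the parent. Section 4.0 says: "The primary safety endpoint will be self-reported adverse effects of tDCS collected after each treatment session". Section 13.0 has an experimenter ask the adolescent about scalp sensations at the end of sessions with tDCS.

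**Who is masked.** Section 10.0 describes computer-controlled sham "allowing all clinical personnel to remain blind" and then says that participants are blind too. Parents are not mentioned there. Parent and child guess the arm only at the follow-up, 14 weeks after the post-treatment visit.

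**The concern.** Behaviour ratings by a parent are subjective, so what the parent believes about the arm can move them. The physical difference between the arms is 30 minutes of 1.5 mA against a brief initial dose that falls to zero. Sensation during the session is therefore the most obvious clue to assignment. Under one sentence of Section 10.0, study staff bring the efficacy rater into an itemised enquiry about that clue, once early in treatment and once at the last session. For most of each session the design keeps the two apart: "Parents and adolescents attend separate concurrent sessions".

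If a belief formed this way affected the ratings, it would most likely favour active, and it would tend to do so on several measures at once because one person completes them all. Agreement across measures would then be weak corroboration. Neither the tests in Section 4.0 nor the descriptive summaries in Section 12.0 could remove such a bias. A guess taken 14 weeks later cannot show what the parent believed when making the primary rating.

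**Working it through.** The plan gives no figure on this point, so the main check is to set the texts side by side. The arithmetic after that is illustrative.

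**1. Is the parent the only described rater?** Yes. Section 10.0 gives all five measures to the parent at baseline and the clinical outcome measures to the parent post-treatment. No teacher, clinician or independent rater is described for them. The fMRI and reaction-time endpoints do not depend on the parent, but they are secondary.

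**2. Does the parent take part in the sensation questionnaire?** The documents disagree.

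| Place | Respondent | When |
|---|---|---|
| Section 10.0, first sentence on the questionnaire | Adolescent and parent | After the second and last sessions |
| Section 10.0, later sentence giving the content | Adolescent | After the second and last sessions |
| Section 4.0 | Self-report | After each session |
| Section 13.0 | Adolescent | End of sessions with tDCS |

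The first row creates the route. It does not say that parent and child answer jointly.

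**3. How close is it to the rating?** In the Section 10.0 schedule, the event after the weekly sessions is the post-treatment visit. The last session is therefore the final scheduled contact before the rating, but the interval is not stated.

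**4. Does a sensation report identify the arm?** The documents suggest it should not do so strongly. Both arms get an initial dose and tingling is said to lessen within minutes (Section 10.0). Section 13.0 puts sensations at about 30-60 seconds after onset. On the other side, Section 10.0 speaks only of most people, and Section 13.0 provides for sensations that a participant cannot manage. Baseline acclimation ramps current to the target level with no distinction by arm, so each child may have a reference for the real sensation.

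**5. Illustration of how much a report could tell.** Let pA and pS be the proportions reporting sensation on active and sham. Both are assumed, because the documents give neither. With 1:1 allocation:

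- P(active given a report) = pA / (pA + pS)
- P(correct guess) = (pA + 1 − pS) / 2

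| pA | pS | P(active given a report) | P(correct guess) |
|---|---|---|---|
| 0.50 | 0.50 | 0.50/1.00 = 0.50 | 1.00/2 = 0.50 |
| 0.60 | 0.50 | 0.60/1.10 = 0.55 | 1.10/2 = 0.55 |
| 0.70 | 0.50 | 0.70/1.20 = 0.58 | 1.20/2 = 0.60 |
| 0.70 | 0.30 | 0.70/1.00 = 0.70 | 1.40/2 = 0.70 |
| 0.90 | 0.30 | 0.90/1.20 = 0.75 | 1.60/2 = 0.80 |

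**6. Illustration of bias in a rating.** Suppose every parent who hears of a sensation infers active, and that this shifts the rating by s standard deviations (SD). Then bias = (pA − pS) × s.

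- Equal rates: 0 × s = 0.
- Difference 0.2, s = 0.25: 0.05 SD.
- Difference 0.6, s = 0.5: 0.30 SD.

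Both inputs are assumptions. The non-zero results lean high for the questionnaire's own contribution. They credit it with the whole cue, and they let every report be read as active although sham participants feel the onset too.

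**7. Scale.** Section 6.0 expects about 10 completers (17 × 0.6 = 10.2), so about 5 per arm. The standard error of a difference in means is √(2/5) = 0.63 SD. Even 0.30 SD is under half of that (0.30/0.63 = 0.47).

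**The case against.** The strongest reply is that the sham is built to reproduce what participants feel. On the protocol's own account, a question about tingling during the session should draw similar answers in both arms and carry no information. That stands as far as it goes: nothing in the documents shows that rates differ. It is an expectation, however, and the plan offers no rates by arm to support it.

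Second, the text does not put parent and child in the same conversation, and the sentence giving the sensation items names only the adolescent. This also stands. It makes the matter one of conflicting wording and not of a settled procedure. Excluding the parent from those items costs little under either reading.

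Third, parent and child are reunited for the last 10-15 minutes of every session and can talk at home, so the questionnaire is not the only route. True, and it means the fix narrows exposure without closing it. The stated purpose of the reunion is homework, though, and an itemised enquiry by staff is more systematic than chance conversation.

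Fourth, parents are asked to guess the arm, which implies that they are meant to be masked. That is a fair inference, but Section 10.0 does not say so.

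A reader might go further and infer that the protocol reveals the arm to the parent immediately before the primary rating and so biases all five measures. The documents do not support this. Sensation is at most suggestive, the rating takes place at a separate visit after an unstated interval, and the knowledge test is likely to be less open to belief than the behaviour ratings.

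**Conclusion.** The concern holds in a limited form. One sentence of Section 10.0 may expose the only described rater of the primary measures to the child's sensation reports, at the last scheduled contact before the post-treatment rating. Other text in Sections 4.0, 10.0 and 13.0 describes the collection differently, so these places must be reconciled. Parents are not named as masked, and their belief about the arm is not checked when the primary rating is made.

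The size of any bias is unknown. It is zero if sensation rates are equal across arms. The range of 0 to 0.30 SD shown above rests wholly on assumed rates and an assumed rating shift, and is not an estimate. Any bias would most likely favour active on the subjective ratings and affect the knowledge test less. In a pilot with about 5 completers per arm, random error would dominate it, although a bias of this kind would not shrink in a larger study using the same procedure.

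This is a cheap improvement. It is not evidence that the blind fails.

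**What to change.** In Section 10.0:

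1. Have the adolescent answer the itching, tingling and burning items without the rating parent present. Apply the same separation to any per-session enquiry that remains once Sections 4.0, 10.0 and 13.0 agree on who is asked and when.
2. Ask the parent separately, at the time now planned, only about past-week headache, neck pain, sleepiness and moodiness. Keeping the timing protects recall for the Aim 1 safety data.
3. State that anything needing action is still passed to the parent at once.
4. Name parents, as raters, among those kept blind.
5. As a complement, collect the parent's arm guess directly after the post-treatment measures are submitted, and not only 14 weeks later.

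The cost is revised wording and one form split in two, with no extra visits or staff. The parent no longer corroborates the sensation items. An earlier guess may also prompt the parent to think about the arm before the 14-week ratings. Those ratings come after the pre- to post-intervention change that Section 4.0 makes primary.

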- **Aim 1.** Establish the safety and feasibility of administering active and sham tDCS with PEERS training in adolescents with ASD. We predict that tDCS administered with 1.5mA current will be safe for participants and tolerable for the majority of participants.
- **Aim 2.** Examine the impact of tDCS in improving social skills and attention to faces. We predict that active tDCS in conjunction with PEERS training will improve social function and attention to faces to a greater degree than sham tDCS plus PEERS training.
- **Aim 3.** Examine the impact of tDCS on neural correlates of social function and attention to faces using functional magnetic resonance imaging (fMRI). We predict that activity in regions that underlie social behavior (e.g., medial prefrontal cortex, temporoparietal junction, fusiform gyrus, amygdala) will increase more in response to social stimuli following active tDCS with PEERS training compared to sham tDCS with PEERS training.

Impact. The present study will address the need to find approaches to enhance social learning in ASD. Social communication difficulties may become especially apparent during adolescence, a time period marked by greater emphasis on social relationships and peer influence. Therefore, the present strategy is to examine the efficacy of a minimally invasive neuromodulatory technique in adolescents in combination with an evidence-based behavioral intervention, PEERS, to enhance social information processing and social interaction, with fMRI markers of neural plasticity before and after intervention.

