12.0 Data Management

Statistical Power. Schneider and Hopp [4] reported an effect size of 2.87 (Cohen's d) for improvement in syntax acquisition in minimally verbal children with autism following 30 minutes of tDCS. This large effect size requires a minimum sample size of 10 subjects, which is comparable to the proposed sample size. However, that study tested a different domain (syntax acquisition) from the present study (social cognition and communication) and sample of children with higher autism severity. Nevertheless, those initial findings are promising indicators of the efficacy of the use of tDCS in ASD.

Data Analysis plan.

- **AIM 1:** We predict that adverse effects and ratings of discomfort, pain, and side effects will be minimal. Only descriptive statistics will be used – frequency of reports of different types of discomfort or pain.
- **AIM 2:** We predict that participants receiving active tDCS will show greater improvement on the Social Responsiveness Scale, the Social Skills Improvement System, the Quality of Play Questionnaire, the Aberrant Behavior Checklist, and the Test of Adolescent Social Skills Knowledge-Revised compared to those receiving sham tDCS. This will be assessed by examining descriptive statistics for each measure..
- **AIM 3:** We predict that after intervention, all participants will show increased social brain network response to faces (v. objects) and to direct (v. averted gaze), with a greater response in those receiving active tDCS. The analysis of fMRI data will include preprocessing (geometric distortion correction, head motion and slice timing correction, spatial (7-mm FWHM) and temporal high-pass (100 sec cutoff) filtering and spatial normalization to MNI space via each subject's high-resolution T1 MPRAGE image. Eight regions of interest (ROIs) will be defined as 10-mm diameter spheres located in left and right medial prefrontal cortex, left and right temporoparietal junction, left and right fusiform gyrus, left and right amygdala, based on prior studies of face processing. In each ROI, percent signal change for faces v. objects or for direct v. averted gaze will be extracted for each subject and for each time point. The effect of tDCS on fMRI signal will be assessed with descriptive statistics.

13.0 Provisions to Monitor the Data to Ensure the Safety of Subjects (if applicable)

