This project involves both a medical device intervention (tDCS) and a behavioral intervention (PEERS training). fMRI scanning, while not an intervention, will be conducted prior to and following 14-weeks of weekly tDCS sessions.

For tDCS, safety of the participants will be monitored during and immediately after delivery of tDCS to the scalp. During tDCS stimulation, subjects have the option of wearing a ski cap which may reduce discomfort. They will be introduced to the ski cap during the tDCS acclimation session on the initial visit. Some subjects may opt not to wear the ski cap, but it will not affect tDCS delivery. At the end of the sessions that involved tDCS delivery, subjects will be asked if they felt or feel any sensations on the scalp where the electrode was and responses are recorded by the experimenter. In [name] experience and other reports in the literature, any sensations of pain, tingling, itching, stinging or irritation follow the onset of stimulation for about 30-60 seconds and do not persist longer than that. If subjects report feelings of sensation or pain that are unmanageable, a local analgesic cream (benzocaine) can be used or the level of current can be reduced to help them complete the session. [name] will be present during all experimental sessions when tDCS is delivered and will be able to monitor for any adverse medical effects.

Adverse effects will be defined by painful sensations that are unmanageable and cannot be alleviated using the procedures outlined above or by persistent reports of high levels of pain by a participant. Although we do not expect this to occur, such events will be reported to the IRB.

For PEERS training, which is a behavioral intervention, the risks are minimal, but include potential discomfort in interacting with other individuals. Should this intervention prove to be too distressful for an individual, the individual will have the option to discontinue the study. Distress would be indicated by persistent withdrawal from or refusal to engage in PEERS activity, persistent protesting, crying or agitation during PEERS sessions. [name] and the research assistant will make the decision as to whether an individual is experiencing distress. When these behaviors lead to removal from the study, these will be reported as adverse events to the IRB.

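### The tDCS tolerance criterion has no term for stopping, a wish to stop is noted only if blamed on tDCS, and no Aim 1 result is committed to by arm

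*Combined protocol and SAP*

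**What the plan says.** Aim 1 (Section 1.0) concerns the safety and feasibility of both active and sham tDCS given with PEERS. Its prediction is about the active dose: "We predict that tDCS administered with 1.5mA current will be safe for participants and tolerable for the majority of participants".

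Three outputs serve this aim, and none mentions arm:
- Section 4.0: "The primary safety endpoint will be self-reported adverse effects of tDCS collected after each treatment session".
- Section 12.0, Aim 1: descriptive statistics only, namely "frequency of reports of different types of discomfort or pain".
- Section 10.0: "We will also report on how many subjects tolerated the procedures".

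For tolerance, Section 10.0 notes reports of irritation or pain, attempts to remove the leads, and "whether a subject wished to discontinue the procedures due to the tDCS (rather than the PEERS training". It does not say who judges the cause. A symptom questionnaire follows the second and last sessions. The criterion is then "We will conclude that tDCS can be tolerated if these effects are experienced less than 25% of the time for a given individual".

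On distress, the PEERS paragraph of Section 13.0 says "Distress would be indicated by persistent withdrawal from or refusal to engage in PEERS activity, persistent protesting, crying or agitation during PEERS sessions", and sends removals for these behaviours to the IRB as adverse events. Section 14.0 (c) and (d) separately name pain from tDCS and severe distress or anxiety during tDCS delivery as grounds for withdrawal.

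On exposure, Section 10.0 gives active participants 1.5 mA for 30 minutes per session. For sham, "All participants receive an initial brief dose; those receiving sham treatment are then automatically decreased to zero by the computer".

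**The concern.** Stimulation and social-skills training happen in the same room at the same time. When an adolescent protests or asks to leave, an observer will often be unable to say which of the two caused it. Noting the wish to stop only after that judgement has been made discards the cases that are hardest to attribute.

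The tolerance criterion is a frequency of effects. Stopping early does not count against it; it only shortens the period over which effects are counted. Someone who finds the procedure unbearable and leaves can therefore look better on it than someone who stays and reports mild tingling.

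The prediction to be assessed concerns 1.5 mA. Sham participants do not receive that current for a full session, so their tolerance says little about it.

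At stake is the reading of the first aim. Section 2.0 (Innovation) makes safety and tolerability the basis for adding tDCS to other behavioural interventions and extending it to younger children.

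**Working it through.** **1. The plan's own figure.** Section 6.0 gives 17 adolescents, about 40% drop-out and 10 complete datasets. 17 × 0.60 = 10.2, and 10 / 0.60 = 16.7, rounded up to 17, so the figure reproduces. Expected non-completers: 17 − 10 = 7, and 7/17 = 41%. These are incomplete datasets; how many will be withdrawals from tDCS, and why, is not stated.

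**2. Who can pass the 25% criterion?** Assume that the share is counted over sessions attended (the plan does not define it). With s symptomatic sessions out of k attended, the rule is s/k < 0.25.
- s = 0 passes at any exit.
- s = 1 passes from k = 5 (1/5 = 20%).
- s = 2 passes from k = 9 (2/9 = 22%).
- s = 3 passes from k = 13 (3/13 = 23%).
- Full course: 3/14 = 21% passes, 4/14 = 29% fails.

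Leaving in distress at session 6 with one symptomatic session gives 1/6 = 17%, a pass. Headache, neck pain, sleepiness and moodiness are asked in Section 10.0 only by the questionnaire after the second and last sessions, so these thresholds do not apply to them. On that questionnaire, a clean second session followed by leaving before the last gives 0/1 = 0%, also a pass.

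**3. Effect on the tolerated share.** Suppose all 17 meet the symptom rule and k of the 7 non-completers left in distress. Ignoring the reason for leaving gives 17/17 = 100%. Counting them as not tolerating gives (17 − k)/17:

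| k | share |
|---|---|
| 0 | 17/17 = 100% |
| 1 | 16/17 = 94% |
| 3 | 14/17 = 82% |
| 7 | 10/17 = 59% |

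The value of k is an assumption; the table shows its full range from 0 to 7.

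**4. Effect of one count over both arms.** Half of 17 is taken as 9 active and 8 sham. Suppose all 8 sham participants tolerate.
- Active 1/9 = 11%: pooled 9/17 = 53%.
- Active 4/9 = 44%: pooled 12/17 = 71%.
- Active 6/9 = 67%: pooled 14/17 = 82%.

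With 8 active and 9 sham, all sham tolerating, active 0/8 to 4/8 (0% to 50%) gives pooled 9/17 to 13/17 (53% to 76%). These are arithmetic bounds, not forecasts. One adolescent moves the active-arm figure by 1/9 = 11 points.

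**5. What a by-arm table can show.** With zero events, the exact 95% upper limit (two-sided Clopper-Pearson) is 1 − 0.025^(1/n): 34% for n = 9 and 37% for n = 8. The table is descriptive at any outcome.

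**The case against.** Several points on the other side have force.

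- **Pooling.** A reader might infer that the plan merges the arms. It does not say so; it is silent. Aim 1 names both arms, the prediction concerns 1.5 mA, and assignment is on file, so the team may well tabulate by arm. What stands is that nothing commits them to it.
- **Distress.** A reader might infer that all session distress is charged to PEERS. That is true only of one paragraph in Section 13.0. Section 14.0 (c) and (d) recognise tDCS pain and distress during delivery, Section 9.0 halts a session on continued protest whatever its cause, and Section 10.0 records lead removal and moodiness with no causal condition. What stands is that none of these is tied to the tolerance criterion or count.
- **Wording of the rule.** The effects in the 25% rule could be read to include lead removal and wishes to stop, and tolerating the procedures is broader than having few symptoms. So it does not follow that a distressed leaver will be counted as tolerating, only that the text permits it.
- **Attribution.** Separating tDCS from PEERS is a fair question for this aim. Participants and clinical personnel are blinded, which limits arm-related bias in the judgement. It does not stop tDCS distress being logged as PEERS distress.
- **Size.** The 53% to 71% range needs every sham participant to tolerate, and nothing in the documents suggests that pattern.
- **Over-correction.** Treating every early stopper as intolerant would misclass those who leave for unrelated reasons. Section 5.0, for example, requires discontinuation after a treatment change. The fix has to allow for this.

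**Conclusion.** The point holds as a minor one. The causal condition on the wish to stop is explicit, the only stated tolerance criterion has no term for stopping, and the distress provisions elsewhere do not feed it. Read literally, an adolescent who leaves in distress can meet the rule, and a count over both arms would not test the prediction about 1.5 mA.

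The possible shift runs from none to 41 points in the tolerated share (100% against 59%), depending on how many of up to 7 non-completers leave in distress. The session thresholds rest on counting over sessions attended; the pooling bounds rest on a 9/8 or 8/9 split with every sham participant tolerating.

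The documents do not show that the count will be too favourable, that the arms will differ, or that the 7 non-completers will be tDCS withdrawals. No formal test or sample-size decision depends on this.

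**What to change.** **Section 10.0.** Record every wish to stop and every episode of persistent distress, whatever the judged cause. Keep the blinded judgement of cause (tDCS, PEERS, other, unclear) as a descriptive column, and say who makes it.

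**Section 12.0, Aim 1.** Report adverse effects, tolerance, wishes to stop and withdrawals (with session number and reason) by randomised arm, with all randomised adolescents as the denominator.

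**Tolerance count.** Count an adolescent who stops because of in-session distress or discomfort as not tolerating, whatever the symptom frequency. List those who leave for clearly unrelated reasons, such as a medication change or scheduling, separately. Add a sensitivity count that treats all early stoppers as not tolerating. State that the table is descriptive.

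**Cost.** One line on the session form, a few sentences in the two sections and a few table rows; no new visit or procedure. The tolerance figure may be slightly less favourable, and with 8 or 9 per arm it cannot establish cause.
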